Choice of Sample Size; Power Considerations– Why 80 adherent participants? The power to detect a difference in the development of postoperative delirium of an the previously reported effect-size²⁴(30% placebo-treated vs. 3% ramelteon-treated) is greater than 0.90, using the current design of 40 participants in each treatment arm and assuming 30% of the placebo-treated group will develop delirium on POD 1 or 2. This design can detect an 80% reduction in delirium (30% placebo-treated vs. 6% ramelteon-treated) with a power of 0.84. A conservative estimate for power for the continuous outcome (DSRS-98R) measuring delirium severity can be derived by conceptualizing the proposed longitudinal analysis as an independent samples t-test. With alpha of 0.05 and a sample size of 80, and with means in the ramelteon and placebo groups of 5.75 and 11.34, respectively (as reported in Hatta, et al), and SDs of 4.16 and 10.96, we would have 84% power to detect that difference. Power for the planned analysis, which includes 3 post-surgery measurements per participant, and controls for baseline measurement and additional covariates would likely be greater.

Data Analysis-Specific Aim 1:

Analysis 1: Odds of postoperative delirium upon immediate recovery will be modeled via logistic regression with treatment assignment as the covariate of interest, and controlling for baseline MMSE, surgical duration and sleep disorders in all randomized participants in a strict intent to treat model and also in a second analysis among the 80 first-dose adherent participants.⁹¹ Odds of delirium on POD's 1 and 2 will be modeled via a Markov logistic regression model⁹² as a function of treatment assignment, baseline MMSE, and mental status on

the previous day, where two transitions are possible: from normal mental status to delirium and/or coma (abnormal mental states) and the reverse. Correlation of mental status on consecutive days for the same individual will be modeled using generalized estimating equations (GEE).⁹² We will fit models with interactions between treatment group and variables hypothesized to predict treatment response, including baseline MMSE and sleep to determine if treatment response varies as a function of baseline predictors.

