Analysis 2: The continuous DRS-98R severity measure of delirium will be modeled via longitudinal linear regression with correlated observations within participants addressed via the method of GEE with treatment assignment as the covariate of interest and controlling for baseline DRS-98R score, MMSE, surgical duration and sleep disorders.

Data Analysis-Specific Aim 2: Risk of a severe adverse event will be modeled as a function of treatment assignment using logistic regression, as will counts of total adverse events using ordinal logistic regression or Poisson regression as appropriate. Counts of each specific type of AE, as a function of treatment assignment will be scrutinized to determine the power needed to study them in future larger-scale trials.

- d. Early stopping rules. This is a pilot study and will continue until 80 adherent participants are recruited. A Data Safety Monitoring Board will review the data at the end of year one or at recruitment of 40 adherent participants (whichever comes first) to review the unblinded (labelled "A" and "B") data for safety of the intervention. Specifically, for the analyses of rates of delirium in the two groups, we will use a Haybittle-Peto boundary such that the alpha for the interim analysis will be 0.001, and the alpha for the final efficacy analysis will be 0.05.

8. Risks

- a. Medical risks, listing all procedures, their major and minor risks and expected frequency.

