Risks associated with the Study Treatment: Ramelteon has FDA approval for use in elderly patients with insomnia. However this agent has never been used peri-operatively in older patients undergoing general or regional anesthesia and we cannot be certain that it will be safe in this setting. Therefore the study aims to test safety of this agent compared to placebo; we will systematically collect daily information on adverse (AE) and serious adverse events (SAE) that occur in each arm of the study. The main potential risk is one of increased incidence of delirium due to the treatment intervention. Other risks associated with the use of ramelteon reported in product labeling include: 1) angioedema and anaphylactic reactions – this risk is extremely rare; 2) worsening of insomnia, or the emergence of new cognitive or behavioral abnormalities that may be the result of an unrecognized underlying psychiatric or physical disorder, such as worsening of depression (including suicidal ideation and completed suicides), hallucinations, bizarre behavior, agitation and mania; 4) amnesia, anxiety and other neuro-psychiatric symptoms may also occur unpredictably, including complex behaviors such as "sleep-driving" (i.e., driving while not fully awake after ingestion of a hypnotic) and other complex behaviors (e.g., preparing and eating food, making phone calls, or having sex) with amnesia for the event; 5) decreased testosterone levels and increased prolactin levels have been reported with long-term use; 7) the use is contraindicated in severe hepatic failure as evidenced by cirrhosis, ascites, portal hypertension and prolonged bleeding times; 8) also contraindicated with the concomitant use of fluvoxamine; and finally 9) caution is to be used when prescribing with other CYP enzyme active agents such as rifampin, fluconazole, and ketoconazole. Other less serious side effects that have been reported in clinical trials include somnolence, fatigue, dizziness, nausea and worsened insomnia.

The following is taken from the ramelteon package insert:

ADVERSE REACTIONS

The following serious adverse reactions are discussed in greater detail in other sections: Severe anaphylactic and anaphylactoid reactions [see Warnings and Precautions (5.1)] Abnormal thinking, behavior changes, and complex behaviors [see Warnings and Precautions (5.3)] CNS effects [see Warnings and Precautions (5.4)]

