6.1 Clinical Trials Experience

Adverse Reactions Resulting in Discontinuation of Treatment

The data described in this section reflect exposure to ROZEREM in 5373 subjects, including 722 exposed for 6 months or longer, and 448 subjects for one year.

Six percent of the 5373 individual subjects exposed to ROZEREM in clinical studies discontinued treatment owing to an adverse event, compared with 2% of the 2279 subjects receiving placebo. The most frequent adverse events leading to discontinuation in subjects receiving ROZEREM were somnolence, dizziness, nausea, fatigue, headache, and insomnia; all of which occurred in 1% of the patients or less.

ROZEREM Most Commonly Observed Adverse Events

Table 1 displays the incidence of adverse events reported by the 2861 patients with chronic insomnia who participated in placebo-controlled trials of ROZEREM.

Because clinical trials are conducted under widely varying conditions, adverse reaction rates observed in the clinical trials of a drug cannot be directly compared to rates in clinical trials of other drugs, and may not reflect the rates observed in practice. The adverse reaction information from clinical trials does, however, provide a basis for identifying the adverse events that appear to be related to drug use and for approximating rates.

Table 1. Incidence (% of subjects) of Treatment-Emergent Adverse Events

Term	Placebo (n= 1456)	Ramelteon 8 mg (n=1405)
Somnolence	2 %	3%
Fatigue	2%	3%
Dizziness	3%	4%
Nausea	2%	3%
Insomnia exacerbated	2%	3%

b. Steps taken to minimize the risks.

We will adhere to the exclusion criteria listed above which will help avoid the recruitment of patients most at risk of side effects and adverse consequences. Patients will be interviewed each day for any side effects and the medical records will be reviewed and the data collected for Aim 2 of the study. A DSMB will review the data as described above and the study will be halted if there is evidence of harm significantly associated with the intervention. We will also inform participants of the risks – particularly when taking the first dose at home. Specifically we will advise them to call 911 or come to an emergency room if, after taking the study drug, they develop any swelling, rash, difficulty or noisy breathing.

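### The one interim look is a safety review, but its only stated criterion for delirium, the named main risk, is a 0.001 level with no separate guideline for harm

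*Combined protocol and SAP*

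**What the plan says.** Section 7.d (Early stopping rules) has the Data Safety Monitoring Board look once, "at the end of year one or at recruitment of 40 adherent participants (whichever comes first"), at arm-level data labelled A and B. The stated purpose is to review the "data for safety of the intervention". The next sentence, which opens with the word Specifically and concerns delirium rates by arm, sets the only numerical criterion: "we will use a Haybittle-Peto boundary such that the alpha for the interim analysis will be 0.001". The end of the trial has its own level, described there as one for efficacy and set at 0.05.

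Section 8.a says: "The main potential risk is one of increased incidence of delirium due to the treatment intervention". Hypothesis 2 in section 2 also lists increased delirium among the harms to be ruled out.

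Section 8.b says that the board will review the data in the way already described and that "the study will be halted if there is evidence of harm significantly associated with the intervention". It gives no level, endpoint or threshold of its own.

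**The concern.** A Haybittle-Peto level is strict so that an early claim of benefit is hard to make and the final test can keep almost all of its alpha. Neither reason applies to harm: stopping because the active arm does worse cannot inflate the type I error for efficacy. Here, though, the 0.001 level is attached to a look described as a safety review, on the outcome named as the main risk, and it is the only interim significance level in the document. A board that looks for the plan's criterion for excess delirium finds 0.001 or nothing.

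The stake is participant protection in the second half of recruitment. Section 8.a concedes that the drug has not been used around surgery in older patients and that its safety there is uncertain, and there is only one planned look.

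**Working it through.** **Inputs**
- Interim level 0.001 and final level 0.05 (7.d). Sidedness is not stated, so both readings are computed.
- Size of the look: at most 40 adherent participants (7.d). The final design is described as "using the current design of 40 participants in each treatment arm" (7.c), so about 20 per arm at the look. The look is smaller if year one ends first. The documents give no accrual forecast, so 10 and 15 per arm are assumptions. Non-adherent participants could raise the number slightly.
- Placebo delirium rate 30% on POD 1 or 2 (7.c). The alternative is 45% in the PACU (4.a, choice of study population).
- The harm scenario, a doubling of the rate, is an assumption of this review.

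**The plan's own figure first.** Section 7.c states power 0.84 for 30% vs 6% with 40 per arm. Arcsine method: h = 2·asin(√0.30) − 2·asin(√0.06) = 0.664; power = Φ(0.664·√(40/2) − 1.96) = 0.844. The unpooled normal formula gives 0.837 and exact enumeration of the chi-square test 0.845. The figure reproduces, so 30% is a fair base rate to use below. The plan states no interim power for harm.

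**What the boundary requires.** With 20 per arm and 6/20 delirious on placebo, two-sided p ≤ 0.001 needs:
- 17/20 on ramelteon by chi-square (p = 0.0004), or
- 18/20 by Fisher's exact test (p = 0.0002; 17/20 gives p = 0.00106).

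The expected result under a doubling, 12/20 vs 6/20, gives Fisher p = 0.11.

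**Normal approximation, 30% vs 60%, 20 per arm.** The pooled rate is 0.45.
- Power = Φ{[0.30 − z·√(2·0.45·0.55/20)] / √[(0.30·0.70 + 0.60·0.40)/20]}.
- Two-sided, z = 3.29: Φ(−1.45) = 7.3%.
- One-sided, z = 3.09: Φ(−1.24) = 10.7%.

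**Exact enumeration.** P(cross) = Σ Bin(x; n, p_placebo)·Bin(y; n, p_ramelteon) over all outcomes with y > x and p ≤ the stated level.

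| Per arm | True rates | Two-sided 0.001, Fisher / chi-square | One-sided 0.001, Fisher / chi-square |
|---|---|---|---|
| 20 | 30% vs 60% | 3.6% / 7.0% | 6.5% / 12.1% |
| 15 | 30% vs 60% | 2.4% / 4.8% | 3.0% / 6.5% |
| 10 | 30% vs 60% | 0.7% / 1.2% | 1.2% / 4.4% |
| 20 | 30% vs 70% | 12.2% / 20.3% | 19.7% / 30.9% |
| 20 | 45% vs 90% (PACU) | 28.8% / 41.4% | 36.8% / 49.7% |

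**For comparison, a one-sided nominal 0.05 guideline for harm**

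| Per arm | Flags 30% vs 60%, Fisher / chi-square | False signal at 30% vs 30%, Fisher / chi-square |
|---|---|---|
| 20 | 46.3% / 58.5% | 2.7% / 5.2% |
| 15 | 35.9% / 51.4% | 2.0% / 5.7% |
| 10 | 24.7% / 41.7% | 1.9% / 5.0% |

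**The case against.** The best defence is that 7.d pairs the interim 0.001 with a final level that it expressly calls an efficacy level. That pairing is ordinary type I error control, so 0.001 may have been meant for early benefit only, with harm left to 8.b and the board's judgement. The board also receives all AEs and SAEs (8.c), participants are asked about side effects daily, and nothing makes the boundary binding or the sole criterion. This stands as a possible reading. On it, however, the plan has no numerical criterion at all for excess delirium, and the link from the safety purpose to the delirium boundary through the word Specifically points the other way. Either way the text needs settling.

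A reader might go further and infer any of four things that the documents do not support:
- *The boundary is symmetric, and 8.b's significantly means p < 0.001.* No sidedness is stated, and 8.b covers harm in general with no level attached. Both are inferences.
- *The rule would almost never flag a doubling.* That is fair at the 30% rate but not at the 45% PACU rate, where crossing is 29-41% at 20 per arm. Section 7.d does not say which of the two primary periods the boundary uses.
- *The board cannot act directionally because the arms are coded.* It sees rates by arm, and nothing bars it from obtaining the key. The plan simply does not say that it may.
- *The plan tells the board that a doubling is acceptable.* No sentence says so.

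It is also true that one look at half of an 80-person pilot has limited sensitivity under any sensible level. A one-sided 0.05 guideline still misses the doubling 41-54% of the time at 20 per arm. No document favours 0.05 over another level.

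**Conclusion.** The concern holds as a gap in the monitoring plan. The look exists for safety, delirium is the named main risk, and the only stated statistical criterion for delirium is 0.001, with sidedness, time point and a harm threshold left open. At 20 per arm and 30% on placebo, that criterion would be met 4-7% of the time (two-sided) or 6-12% (one-sided) if ramelteon truly doubled delirium. An early year-one look at 10-15 per arm lowers the two-sided figure to about 1-5%. The 45% PACU rate raises it to 29-41% at 20 per arm.

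These figures rest on equal arms, simple two-group tests, a doubling as the harm scenario and, for the early look, assumed arm sizes. The final efficacy inference is not affected. This should be fixed because it is a cheap improvement in protection; it is not a defect that invalidates the trial.

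**What to change.** In 7.d, 8.b and any board charter:
1. State that 0.001 applies to stopping early for efficacy only, and give its sidedness.
2. Add a separate, directional, non-binding statistical guideline for excess delirium on the active arm, at a less stringent level chosen by the sponsor and the board. One-sided 0.05 is an example, not a recommendation over other levels.
3. Name the delirium time point (PACU, POD 1-2, or both) to which each criterion applies.
4. Reconcile 8.b with 7.d by saying that this guideline is what significantly associated means for delirium.
5. State that the board may obtain the A/B key.

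At the example level the guideline would flag the doubling from 30% to 60% with probability 46-59% at 20 per arm and 25-42% at 10 per arm. The cost is wording plus a false harm signal in roughly 2-6% of trials with no true difference, which the board may override. Sample size and the final alpha of 0.05 do not change.

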6.1 Clinical Trials Experience

Adverse Reactions Resulting in Discontinuation of Treatment

The data described in this section reflect exposure to ROZEREM in 5373 subjects, including 722 exposed for 6 months or longer, and 448 subjects for one year.

Six percent of the 5373 individual subjects exposed to ROZEREM in clinical studies discontinued treatment owing to an adverse event, compared with 2% of the 2279 subjects receiving placebo. The most frequent adverse events leading to discontinuation in subjects receiving ROZEREM were somnolence, dizziness, nausea, fatigue, headache, and insomnia; all of which occurred in 1% of the patients or less.

ROZEREM Most Commonly Observed Adverse Events

Table 1 displays the incidence of adverse events reported by the 2861 patients with chronic insomnia who participated in placebo-controlled trials of ROZEREM.

Because clinical trials are conducted under widely varying conditions, adverse reaction rates observed in the clinical trials of a drug cannot be directly compared to rates in clinical trials of other drugs, and may not reflect the rates observed in practice. The adverse reaction information from clinical trials does, however, provide a basis for identifying the adverse events that appear to be related to drug use and for approximating rates.

Table 1. Incidence (% of subjects) of Treatment-Emergent Adverse Events

Term	Placebo (n= 1456)	Ramelteon 8 mg (n=1405)
Somnolence	2 %	3%
Fatigue	2%	3%
Dizziness	3%	4%
Nausea	2%	3%
Insomnia exacerbated	2%	3%

b. Steps taken to minimize the risks.

We will adhere to the exclusion criteria listed above which will help avoid the recruitment of patients most at risk of side effects and adverse consequences. Patients will be interviewed each day for any side effects and the medical records will be reviewed and the data collected for Aim 2 of the study. A DSMB will review the data as described above and the study will be halted if there is evidence of harm significantly associated with the intervention. We will also inform participants of the risks – particularly when taking the first dose at home. Specifically we will advise them to call 911 or come to an emergency room if, after taking the study drug, they develop any swelling, rash, difficulty or noisy breathing.

The clinical team (Attending Surgeon - eg., Co-Investigators: [name], [name], [name] and the Chief of Anesthesiology - eg., Co-Investigator [name]) will be notified by the study team should any patient be found to be delirious (thereby ineligible) during the screening process for the study. The Attending Surgeon (or his designee) will be responsible for contacting the patient's family and arranging subsequent follow-up of the patient - either in an emergency setting, in the clinic, or through early admission to hospital. The precise recommendation will be informed by the clinical status of the patient.

- c. Plan for reporting unanticipated problems or study deviations.

All AE's and SAE's will be reported to the IRB and the DSMB in keeping with rules of the Johns Hopkins Institutional Review Board. As noted above – data on adverse effects will be collected each day of the study.

- d. Legal risks such as the risks that would be associated with breach of confidentiality.

As with any study incorporating research as a part of clinical care, there is a small but real risk of unintentional release of HPI. We will make every effort to secure data and study records under lock and key and encryption in keeping with institutional standards to prevent this from occurring.

- e. Financial risks to the participants.

The financial risks to the participants related specifically to this protocol are minimal.

9. Benefits

- a. Description of the probable benefits for the participant and for society.

While there may be no clear benefit for those participants who take part, this study is an important next step in the discovery of pharmaceutical agents in postoperative delirium prevention. **A positive outcome may help relieve suffering of many patients in our healthcare system in the future and stimulate further inquiry delineating the role of melatonin in the genesis of delirium, potentially benefiting society.**

10. Payment and Remuneration

- a. Detail compensation for participants including possible total compensation, proposed bonus, and any proposed reductions or penalties for not completing the protocol.

